6.7.2 Time windows for every RECIST assessment

In order to identify whether consecutive imaging timepoints are missing for a given patient, a nominal time point [8, 16, 24, 32, 40, 48 weeks and every 12 weeks thereafter] will be assigned to each and every image. This is achieved by creating windows for every RECIST 1.1 assessment. The windows are defined in Table 6.7.2: 1 below. Day 1 corresponds to date of randomisation for the Phase II part (for the Phase Ib part it corresponds to the date of first drug intake of xentuzumab).

Table 6.7.2: 1 Nominal time-points and windows for imaging

Nominal time-point [weeks from start of therapy]	Due date of scans [days]	Window [days]
8	57	1 to =< 85
16	113	86 to =< 141
24	169	142 to =< 197
32	225	198 to =< 253
40	281	254 to =< 309
48	337	310 to =< 379

Proprietary confidential information © 2018 Boehringer Ingelheim International GmbH or one or more of its affiliated companies

Table 6.7.2: 1 Nominal time-points and windows for imaging (cont.)

Nominal time-point [weeks from start of therapy]	Due date of scans [days]	Window [days]
60	421	380 to =<463
72	505	463 to =<547
every 12 weeks interval	etc (1)	etc (1)

(1) Due date of scans = (nominal time point * 7) + 1. To calculate the lower bound of the window, use the middle point between the due date of the previous time point and the current due date + 1. To calculate the upper bound of the window, use the middle point between the due date of the next time point and the current due date.

If a patient does not have an image in one of the windows described above, she will be said to have 'missed an assessment' for that timepoint. In case a patient has more than one assessment in one window, the assessment with the latest outcome will be used for the analysis unless a PD has been recorded earlier then PD will be used.

7 PLANNED ANALYSES

The labelling and display format of statistical parameters will follow BI standards [\(7\)](#).

Unless otherwise specified, outputs will be displayed separately for each part of the trial.

Descriptive statistics for continuous variables will generally contain N (number of patients in that patient set with non-missing values), Mean, Standard Deviation, Minimum (Min), 25th percentile (Q1), Median, 75th percentile (Q3), Maximum (Max). In general, means, standard deviations, medians, Q1 and Q3 will be presented to one more decimal place than the raw data. Minima and maxima will be presented to the same number of decimal places as the raw data.

For time-to-event analysis tables, the set of statistics is: number of patients [N (%)], Number of patients with event [N (%)], Number of patients censored [N (%)], <Time to event> [months] followed by Q1 (25th percentile), Median, Q3 (75th percentile). If not specified otherwise, the duration as well as time to event will be displayed in months.

Tabulations of frequencies for categorical data will include all possible categories and will display the number of observations in a category as well as the percentage (%) relative to the respective treatment group total. Percentages will be rounded to one decimal place.

In general a category “missing” will be displayed, if there are missing data for the corresponding variable. Percentages will also generally be based on all patients in the respective patient set whether they have non-missing values or not.

The primary analysis will include all treated (Phase Ib) or randomised patients (Phase II), following the ITT approach (as specified in [Section 6.3](#)).

The analyses for the primary endpoint of PFS as well as best overall response, OR, time to OR, duration of OR, DC, duration of DC, time to progression, tumor shrinkage, tumor size as well as the [REDACTED] will be based on data obtained until November 25th 2016. A sensitivity analysis for the primary endpoints PFS will be performed using all data. Analyses of other RECIST based endpoints will also only utilise data obtained from assessments scheduled until November 25th 2016. For overall survival all available data will be used.

Analyses of AEs for the phase II will be split in two parts. The first part considers all AEs with onset date on or before the cut-off date 9th of December 2016 (28th of October 2016 + length of REP (42 days)) and AEs with onset date after 9th of December 2016. Details are given in [Section 7.8.1](#).

Sort order for general categorical variables: If categories correspond to the collected categories on the eCRF and the table shells do not explicitly specify the ordering, the “default ordering” defined by the eCRF is to be used in such cases. If categories are derived the ordering as specified in the table shell document should be used; in general ordinal data (e.g. categorised continuous data) are to be displayed in ascending order.

The denominator of the main categories is defined by the number of patients in the used patient set. The main categories define the denominators of the subcategories. Subcategories should be indented and “[N (%)]” to be displayed only for the main category.

If a table includes only categorical data, “[N (%)]” is to be displayed in the column header.

Proprietary confidential information © 2018 Boehringer Ingelheim International GmbH or one or more of its affiliated companies

In general, a “Total” column will be displayed in section 15.1 (Trial subjects) of the CTR. In Sections 15.2 and 15.3 of the CTR, a “Total” column will be displayed in Phase Ib outputs, but not in Phase II outputs.

Abbreviations (e.g., Wors.) or acronyms (e.g., PD) should not be displayed in tables and patients data listings without any explanation. They will be either spelled out in the table or explained in footnotes (whatever is more reasonable from the programming point of view).

If applicable, conversion from days to weeks, months and years will be as follows:

- Weeks = days \div 7
- Months = days \times 12 \div 365.25
- Years = days \div 365.25

7.1 DEMOGRAPHIC AND OTHER BASELINE CHARACTERISTICS

Only descriptive statistics are planned for this section of the report.

7.1.1 Disposition of patients

For patient disposition the standard descriptive table from the EOT/CSD (Company Standard Displays) catalogue will be populated. Additionally, patients with discontinuations by initial treatment and the reasons will be listed and tabulated, overall and for each treatment separately. The same output will also contain an overview of discontinued and non-discontinued, as well as completed and non-completed patients. In Appendix 16.1.9.2, a disposition table by country will be produced.

Disposition of patients will also be displayed by visceral involvement.

7.1.2 Important protocol violations

A table and a listing of patients with important protocol violations based on [Table 6.2: 1](#) will be created in Section 15.1.3 and Appendices 16.2.3 and 16.1.13.1 (if needed) respectively, of the CTR.

7.1.3 Demographic and other baseline characteristics

Standard descriptive analysis and summary tables for all patients treated by initial treatment will be created for demographic data, oncological history and baseline conditions.

For the subgroup of the first tier visceral involvement demographic characteristics as well as oncological history will be provided as well.

7.2 CONCOMITANT DISEASES AND MEDICATION

Only descriptive statistics are planned for this section of the report. Concomitant diseases will be coded similarly as adverse events based on the most current Medical Dictionary for Regulatory Activities (MedDRA) version. Concomitant therapies will be coded according to World Health Organisation - Drug Dictionary (WHO-DD). Concomitant therapies (CT) will be classified according to the Anatomical, Therapeutic, Chemical (ATC) classification system. The third ATC level will be used to categorise CTs by therapy type. In situations

Proprietary confidential information © 2018 Boehringer Ingelheim International GmbH or one or more of its affiliated companies

where a medical product may be used for more than one equally important indication, there are often several classification alternatives. As appropriate, patients receiving CTs with more than one possible ATC level-three category will be counted more than once; footnotes will clarify this possible double counting in tables.

Concomitant medications will be presented according to whether they are concomitant with the reception of study medication, or whether they were given prior to study medication. In case start and stop dates of the medications are completely missing, they are assigned as given prior to study medication.

7.3 TREATMENT COMPLIANCE

Compliance was not analysed separately by treatment received. The number of missed doses of any medication as recorded on the eCRF will be listed by patient.

7.4 PRIMARY ENDPOINTS

7.4.1 Phase Ib

The primary endpoints are the MTD and the occurrence of DLT. The MTD is determined from the occurrences of DLTs during the MTD evaluation period (this period is defined in [Section 5.1.1](#)). An overall summary of the DLTs (see CTP Section 5.2.6 for definitions of DLT) which occurred during the MTD evaluation period and the on-treatment period will be provided for each dose cohort.

Patients that were treated but replaced for the MTD evaluation (see CTP Section 3.3.5) will be excluded from the MTD determination. Replacement of patients will be determined on a case by case basis; exclusion of these patients from the MTD evaluation will be confirmed by the trial team at the report planning meeting prior to database lock.

A listing of patients with DLTs by initial treatment will be performed. A plot with an overview of the phase Ib escalation part (showing the patients and their doses, replaced patients as well as patients with DLTs) will be displayed.

At the end of the dose escalation phase, a safety analysis will be performed to determine the RP2D. The results will be documented for internal use and communication with the participating investigators. (see also in [Section 9.1](#))

7.4.2 Phase II

The primary analysis will be conducted for all patients of the randomised set in the Phase II part of this trial; following the changes described in [Section 4.2](#), only response assessments until the cut-off date of 25th November 2016 will be used (as described in protocol). For the derivation of the censoring rules, the status of the patient (e.g. treatment ongoing / discontinued / new anti-cancer therapy) will be taken as of the cut-off date. This means if a patient was ongoing at the cut-off date, its PFS with cut-off will be censored at last assessment before the cut-off, with reason treatment ongoing.

PFS by investigator's assessment is the primary endpoint and will be assessed based on the Kaplan-Meier method for each treatment arm separately. Point estimates together with confidence intervals (CIs) (based on Greenwood's method) will be provided for median PFS.

Proprietary confidential information © 2018 Boehringer Ingelheim International GmbH or one or more of its affiliated companies

An estimation of the effect on PFS of xentuzumab plus exemestane plus everolimus compared to the effect on PFS of exemestane and everolimus will be given by the hazard ratio (HR) and its 95% CI using a stratified Cox proportional hazards model (using visceral involvement as stratification factor). The validity of the underlying assumptions of this model will be checked. HRs < 1 will favour treatment with xentuzumab plus exemestane plus everolimus; p-value from the two-sided log-rank test will be also displayed but it should be emphasised here that this is only to be understood in an exploratory way. The Breslow method for handling ties will be used. The censoring rules for PFS are as stated in [Section 5.1.2](#).

7.4.2.1 Subgroup analyses for PFS

Subgroup analyses will be conducted for the primary endpoint of the Phase II part (PFS) as follows:

For each of the subgroups specified in [Section 6.4](#) HRs will be produced in order to investigate the subgroups. HRs will be obtained from the models fitted for each level of the baseline covariate. All Cox models will be adjusted (but not stratified, due to the low number of patients) with the stratification factor visceral involvement. However, in the case when investigating the stratification factor, the model will not be adjusted.

To provide a statistical framework for interpretation of the consistency of the treatment effect interaction p-values will be created using a model adjusted for treatment, stratification factor, subgroup and treatment by subgroup interaction. However, in the case when investigating the stratification factor, the model will not be adjusted additionally for this factor. For the evaluation of the interaction between treatment effect and the baseline variables, all subgroups showing an interaction p-value ≤ 0.1 will be considered as potential subgroup and might be investigated in more detail.

Forest plots will be produced for the graphical interpretation of subgroup analyses.

Standardized effect size plot

Furthermore, standardized effect size plots (as described below) will be applied to the two tiers (defined in [Section 6.4](#)). These may also be provided separately, if deemed useful.

Generally, the higher the number of subgroup analyses performed, the higher the probability of a positive finding by chance (pure randomness) alone. Therefore, a standardized effect size evaluation will be performed in addition in order to consider the number of subgroups, the correlation between the subgroups, the observed effect size within the subgroup and the sample size of the subgroups.

Standardized effect size plots will be produced to identify on a permutation basis the minimum and maximum difference from the null hypothesis (no treatment effect overall) across all subgroups. This illustrates how extreme the results are expected to be by chance given the number, the size, and the correlation structure of subgroups.

For each subgroup the observed standardized effects will be calculated and compared to permutation-based confidence bands (5 and 95% percentiles) taking into account the multiplicity issues based on permuted datasets (10.000 times). For each permuted dataset the standardized effects for each subgroup will be calculated and thereof the maximum of the absolute values of the standardized effects are received. Repeating this 10.000 times, we will

Proprietary confidential information © 2018 Boehringer Ingelheim International GmbH or one or more of its affiliated companies

use the 90th percentile B of the maximum absolute effects which provides us with a 90%-confidence band $[-B; B]$. Any subgroups showing an adjusted p-value outside this 90%CI are identified. In a stepwise procedure, those subgroups are then excluded and the standardized effect method is applied to the remaining subgroups in order to again identify the minimum and maximum difference from the null hypothesis (no treatment effect overall). The procedure ends in case no selected subgroup for the maximum or minimum is identified. If deemed appropriate, subgroups with missing values may be excluded from the calculation of the standardized effect size plot.

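### SAP 7.4.2.1 flags subgroups by setting an adjusted p-value against a band for standardized effects, which contradicts the comparison announced in the same paragraph

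*SAP*

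**What the plan says.** The part of SAP 7.4.2.1 on the standardized effect size plot sets out a permutation method for the PFS subgroups. It opens with the comparison to be made: "For each subgroup the observed standardized effects will be calculated and compared to permutation-based confidence bands". In each of 10,000 permuted datasets, "the standardized effects for each subgroup will be calculated and thereof the maximum of the absolute values of the standardized effects are received". The SAP will then "use the 90th percentile B of the maximum absolute effects which provides us with a 90%-confidence band", written [-B; B].

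The decision sentence follows: "Any subgroups showing an adjusted p-value outside this 90%CI are identified". Subgroups identified in this way are removed and the method is applied again to the rest. The stopping rule is: "The procedure ends in case no selected subgroup for the maximum or minimum is identified".

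Earlier in 7.4.2.1 the SAP gives the aim, which is to allow for the number of subgroups, their correlation, "the observed effect size within the subgroup and the sample size of the subgroups". The same section also plans hazard ratios by subgroup, forest plots, and interaction p-values with a separate screen at 0.1.

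**The concern.** The paragraph names two different quantities for one comparison. Its opening sentence puts the observed standardized effect against the band, and its decision sentence puts an adjusted p-value there. The band is made from absolute standardized effects, so only the first comparison is on a common scale. The visible text of 7.4.2.1 does not say how the adjusted p-value is obtained.

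The decision sentence controls which subgroups are removed and therefore when the stepwise procedure stops. In the visible text this is the only PFS subgroup rule that allows for multiplicity; the interaction screen at 0.1 is unadjusted. A programmer who follows the decision sentence gets a different output from one who follows the opening sentence.

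**Working it through.** The SAP gives no value of B, so there is no stated figure to reproduce.

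**Inputs.** From SAP 7.4.2.1: the statistic is the maximum absolute standardized effect, the cut is its 90th percentile B, there are 10,000 permutations, and the quantity in the decision sentence is an adjusted p-value, which lies between 0 and 1. From Protocol 7.3.1, for illustration: 150 patients and about 90 PFS events. Assumed: the number of subgroups, because SAP 6.4 is not in the text available, and their prevalence.

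**Step 1, the lower limit.** A p-value is never negative, so it cannot fall below -B on any scale.

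**Step 2, the upper limit if the effect is estimate/SE.** For one subgroup the 90th percentile of |Z| is z(0.95) = 1.645. This equals the 5% and 95% percentiles of Z, so the SAP's two descriptions of the band agree in that case. A maximum over several subgroups is at least as large as the value for any one of them, so B is at least about 1.645 whatever the correlation. For K independent subgroups B = z(1 - (1 - 0.9^(1/K))/2):

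| K | 1 | 2 | 5 | 10 | 20 | 30 | 40 |
|---|---|---|---|---|---|---|---|
| B | 1.645 | 1.95 | 2.31 | 2.56 | 2.79 | 2.92 | 3.01 |

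Every p-value is at most 1 and so lies inside [-B; B]. Nothing is flagged, and the stopping rule is met at the first step.

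**Step 3, permutation check.** Treatment labels were permuted 10,000 times in simulated data (150 patients, 90 events, overlapping two-level subgroups, log-rank-score z statistics), with true hazard ratios of 1.0, 0.72 and 0.30, giving 15 runs. The adjusted p-value was taken as the share of permutations in which max|z| was at least the observed |z|. Results at a hazard ratio of 0.30:

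| Subgroups | B | Largest observed absolute z | Flagged, effect outside [-B; B] | Flagged, adjusted p outside [-B; B] |
|---|---|---|---|---|
| 2 | 1.93 | 3.88 | 2 | 0 |
| 6 | 2.29 | 2.77 | 3 | 0 |
| 10 | 2.44 | 5.06 | 9 | 0 |
| 20 | 2.65 | 5.66 | 19 | 0 |
| 30 | 2.74 | 4.74 | 21 | 0 |

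At 0.72 the effect rule flagged 1 of 30 subgroups in the largest run and none in the others; at 1.0 it flagged none. The literal rule flagged none in all 15 runs. Flagging when the adjusted p-value is at most 0.10 gave the same count as the effect rule in all 15.

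**Step 4, the alternative scale.** If the effect were an unscaled log hazard ratio, the one-subgroup limit would be about 1.645 × 2/√d for d events: 0.736 at 20 events, 0.490 at 45, 0.347 at 90. In the runs above B on this scale was about 0.6 to 0.9. The literal rule would then flag large p-values. As an illustration, take the adjusted p-values from the 10-subgroup runs (computed on the z scale). With a hazard ratio of 1.0 they ran from 0.9492 to 1.0000 against B = 0.79, so all ten would be flagged. With 0.30 they ran from below 0.0001 to 0.6411 against B = 0.78, so none would be.

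**The case against.** The strongest reply is that the intended rule is already in the SAP. The opening sentence of the paragraph compares standardized effects with the band, and the stepwise text applies the same method to the remaining subgroups. The decision sentence may be loose shorthand for significance at an adjusted 10% level, which Step 3 shows to be the same rule. This stands. The intent is recoverable, and an analyst who compares effects with the band follows text that is already there. It would be too strong to say that such an analyst has left the pre-specified rule.

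A reader might infer three further things that the documents do not support:

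- That no subgroup could be flagged under any definition. This needs B to be at least 1, and the visible text does not define the standardized effect. The stated aim of allowing for subgroup sample size favours estimate over standard error but does not settle it.
- That the SAP nowhere defines an adjusted p-value. Section 6.4 is not in the available text, and SAP 6.3 refers to a technical TSAP that cannot be seen. Only its absence from the visible 7.4.2.1 can be stated.
- That the literal rule would report a consistent treatment effect whatever the data. The SAP assigns consistency to the interaction p-values. The band refers to a null of no overall treatment effect, so an empty result would say only that nothing was flagged under that null.

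What survives the reply is that the operative sentence conflicts with its own paragraph and gives a wrong result on either scale if it is programmed as written.

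**Conclusion.** The point holds as a wording error in a decision rule. On the estimate/SE reading the literal rule flags nothing and stops at once, because B is at least about 1.645 and a p-value is at most 1. That conclusion needs only B ≥ 1; the assumed number of subgroups, prevalence and event count affect the illustration alone. On an unscaled log hazard ratio with B below 1, the rule selects the subgroups with the least evidence of an effect.

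The importance is low. Protocol 7.1 and 7.2 plan only descriptive and exploratory analyses, and the fault touches only this subgroup screen. The primary PFS hazard ratio and its interval, the subgroup hazard ratios, the forest plots and the interaction screen are unaffected, and the plotted effects remain visible to the reader.

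**What to change.** Replace the decision sentence in SAP 7.4.2.1 with: *Any subgroup whose observed standardized effect lies outside [-B; B] is identified.* An equivalent wording is a single-step permutation-adjusted p-value of at most 0.10; if that form is used, define the adjusted p-value as the share of permutations whose maximum absolute standardized effect is at least the observed absolute value. State that the standardized effect is the log hazard ratio divided by its standard error, and that the same statistic is used at every step of the stepwise procedure.

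The cost is a sentence or two in the SAP. No data collection, sample size or primary analysis changes.

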7.4.2.2 Sensitivity analyses for PFS

Using all available data

As a sensitivity analysis, the PFS analysis (without subgroup analysis) will be repeated, using all available radiological response assessment data (including those measured after the cut-off date from the primary analysis). As for the primary analysis, the randomised set will be used.

Stratification factor based on IRT

The PFS analysis will be repeated, using data from IRT stratification (for the factor visceral involvement) instead of using data collected in the CRF. As for the primary analysis, only response assessments until the cut-off date of 25th November 2016 will be used.

